**20. Provisions to Monitor the Data to Ensure the Safety of Participants**

No DSMB will be convened given the minimal risks involved in this study.

**21. Provisions to Protect the Privacy Interest of Participants**

To address the risk for loss of confidentiality associated with conducting research and collecting data, rigorous procedures will be in place to ensure the security and confidentiality of the dataset during analyses. As noted previously, all data will be coded when stored on a secure Emory University server using RedCap. Access to the data will be limited to the study PI, co-investigators, approved research personnel. The PI and collaborators have completed in depth online and in-person training in human subjects training at Emory University. The PI will continue to participate in the Office of Nursing Research's monthly colloquia on conducting ethical research and the responsible conduct of research. These monthly lectures and seminar series are led by research experts across the University and address a wide array of maintaining ethical standards and quality throughout the research process. All data will be reported in the aggregate in peer-reviewed publications to ensure participant privacy. Data shared with the funder and other collaborators will be identified and no PHI will be collected. All participants will receive a handout with the contact information of employee health services to help address any symptoms they may be experiencing. Symptom level data will not be analyzed in real time and therefore cannot be monitored to inform individuals connecting to services.

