## 1. Study Summary

Study Title	Implementing and Evaluating the Effect of Personalized Pain Coaches After Orthopaedic Surgery for Patients with Sports Medicine Injuries to Improve Postoperative Outcomes
Study Design	Three arm randomized control trial
Primary Objective	The objective of this randomized controlled trial is to examine how the integration of a trained Life Care Specialist improves postoperative recovery related to patient-reported pain outcomes following orthopaedic injury
Secondary Objective(s)	Examine how the integration of a trained Life Care Specialist improves postoperative recovery related to opioid utilization and objective functional outcomes following orthopaedic injury
Research Intervention(s)/Interactions	The LCS will work with the patient to create a pain management plan focused on behavioral education. The LCS interventions can encompass all, but not limited to, the information included below: 

• Opioid Risk Education

• Therapeutic Intervention

• Clinical Pain Coordination

Study Population	Orthopaedic patients seen at Emory and Grady
Sample Size	150
Study Duration for individual participants	~90 days
Study Specific Abbreviations/ Definitions	LCS, Life care specialist
Funding Source (if any)	National Football League (NFL)

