## **6. Procedures Involved**

If the patient meets inclusion criteria, the CRC will visit patient during their preoperative consult or call the referred patient through his/her number listed on Epic. If unable to visit in person and reach through call, the CRC will message patient through the Secure Chat feature on Epic to potentially schedule an e-consent. If informed consent is obtained, they will be enrolled into REDCap for randomization into one of the three groups. A simple number generator, within RedCap, will sequentially randomize participants into control or one of the two intervention arms. After consenting, enrolling, and allocation, research staff will administer a battery of measures on tablets stored in REDCap, or on paper and later transcribed into REDCap to all participants. In the event the participant is unable to complete study measures during the clinic visit they will be emailed a secure link to RedCap to complete the consent form and the study measures.

Those randomized to the intervention will either meet with a Life Care Specialist for 1 hour before surgery, either in person or via Zoom® during their preoperative consult or at another time no later than 24 hours before surgery.

During their follow up visits with the surgical team at Grady Hospital or Emory Orthopaedics scheduled at 2-weeks, 6-weeks, and 3-months postoperatively participants will again be provided a tablet to complete outcome measures. In the event participants cannot physically travel to the clinic, appointments will be conducted over video conferencing and participants will have the option to be emailed the outcome measures to complete. If they are unable to complete the measures via email within 72-hours study staff will call participants to complete measures over the phone. If no response, paper copies of the measures will be mailed to participants with prepaid

**Protocol Title:** Implementing and Evaluating the Effect of Personalized Pain Coaches After Orthopaedic Surgery for Patients with Sports Medicine Injuries to Improve Postoperative Outcomes

---

postage to return them or QR code post cards to complete surveys. There is a one week window for the first follow up visit, two week window to complete measures for the second follow up study visit, and four weeks for the last study visit. Study staff will call participants and offer to video conference with them within 48 hours of surgery to review how to wear the actigraphy device and use the MEMS cap.

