The following data will be collected on the patients:

- Demographics: Name, date of birth, date of admission, gender, ethnicity, body mass index, zip code, insurance
- Health record data: Data abstraction from health records include injury severity score, mechanism, drug screen on arrival, alcohol screen, pre-existing conditions, inpatient complications, surgical time, regional anesthesia, medication received, and opioid medication doses discharged with.
- Comprehensive social determinants of health (SDOH) survey: This measure includes assessments of housing, financial stability, education, community context, intimate partner violence, health literacy, prior personal and family substance use, a validated measure of post-traumatic stress disorder, adverse childhood experiences, and mental illness. This has been utilized in prior research by this team and takes approximately 20-25 minutes to complete.
- Revised Opioid Risk Tool (ORT): The ORT is a self-reported measure used to ascertain a participant's current and future risk of aberrant drug-related behaviors in patients prescribed opioid therapy.(Cheatle et al., 2019; Webster & Webster, 2005) Recently a shortened revised ORT was recently developed and will be used in this study.(Cheatle et al., 2019) Across 9-items, this tool assesses family history of substance abuse, personal history of substance abuse, age range, and current psychological disease. Each endorsement is scored as 1 for a total score ranging from 0 to 9. Scores of 3 or greater are predictive of high risk for opioid use disorder.
- PTSD screener: This screener is a 5-item screening tool used to assess previous exposure to traumatic events and subsequent presence of the DSM-V diagnostic criteria for PTSD.(Prins et al., 2016) Each item respondents report "Yes" to can be scored as a point so that a minimum of 3 points is used in primary care settings to be considered probable PTSD.

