#### **10. Inclusion and Exclusion Criteria**

We will recruit 150 participants from the orthopaedic sports medicine service at Grady and Emory Healthcare for this study. Individuals between 15–45 years old, scheduled for orthopaedic surgery due to sports medicine injuries (e.g., anterior cruciate ligament tears, meniscus injury, rotator cuff injury, etc.), and those who are actively employed or full-time athletes prior to injury will be eligible. Individuals unable to provide consent, those undergoing revision procedures, individuals without access to an internet connected device, and individuals who are unemployed or retired at time of injury will be ineligible. No one will be excluded from participation based on gender, race, or ethnicity. Individuals who are incarcerated or pregnant will not be eligible. Individuals unable to consent and those unable to communicate in English will be excluded since all surveys are validated in English.

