#### **12. Vulnerable Populations**

Our research may involve teenagers between the ages of 15 to 17 years. If so, proper assent and parental consent will be obtained.

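### The one symptom contact named for all arms, an employee health service, may be unusable for some of these surgical patients

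*Combined protocol and SAP*

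**What the plan says.** Section 21 (Provisions to Protect the Privacy Interest of Participants) contains the instruction: "All participants will receive a handout with the contact information of employee health services to help address any symptoms they may be experiencing". The next sentence reads: "Symptom level data will not be analyzed in real time and therefore cannot be monitored to inform individuals connecting to services".

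The people who will receive that handout are defined elsewhere. Section 1 (Study Summary) gives the study population as "Orthopaedic patients seen at Emory and Grady". Section 10 (Inclusion and Exclusion Criteria) sets the age range at 15 to 45 and the occupational condition: "those who are actively employed or full-time athletes prior to injury will be eligible". Section 12 (Vulnerable Populations) adds: "Our research may involve teenagers between the ages of 15 to 17 years".

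**The concern.** An employee health service normally serves the staff of a particular employer. The participants here are patients. Their link to Emory or Grady is that they have surgery there, not that they work there. If the instruction is followed literally, a participant with no access to the service receives a contact that does not help. A 16-year-old athlete is the clearest example.

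What is at stake is participant protection, not inference. Section 6 says that "research staff will administer a battery of measures on tablets stored in REDCap, or on paper and later transcribed into REDCap to all participants", and the social-determinants survey it lists covers "intimate partner violence, health literacy, prior personal and family substance use, a validated measure of post-traumatic stress disorder, adverse childhood experiences, and mental illness". Such questions can cause distress, and surgery itself produces symptoms. Because Section 21 says that study symptom data will not be used in real time to connect people with services, the handout should point somewhere the recipient can go.

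**Working it through.** No arithmetic applies: the protocol gives no figure on this point and none can be derived. The check sets the instruction beside the population, and then looks for another symptom contact that covers all arms.

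**1. Does eligibility imply access to an employee health service?**
- Section 10 requires employment or full-time athlete status before injury, and excludes people unemployed or retired at the time of injury. It names no employer.
- The condition is fixed at the time of injury. It does not establish access to an employer's service during the 3 months after surgery.
- Full-time athletes qualify without any other employment, and participants may be as young as 15.
- Section 21 does not say whether the service is Emory's, Grady's or that of the participant's own employer, or whether non-employees may use it.

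Eligibility therefore does not guarantee access. Some participants may have it through their own employer, and others may not.

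**2. Is another contact named for symptoms in all arms?**
- Section 5 (Study Intervention/Design): directed referrals for mental-health and substance-use needs are a component of the two Life Care Specialist arms.
- Section 3 (Background): the Life Care Specialist is described as a point of contact, which again applies only to those two arms.
- Section 5, standard of care (which the specialist arms also receive): a prescribing protocol, discharge instructions with tapering advice, and links on opioid misuse, overdose prevention and disposal. No symptom contact is named.
- Section 6 (Procedures Involved): surgical-team visits at 2 weeks, 6 weeks and 3 months, described as occasions for outcome measures. It also says "Study staff will call participants and offer to video conference with them within 48 hours of surgery", for the purpose of reviewing the actigraphy device and the MEMS cap.
- Section 15 (Withdrawal of Participants): email to the investigator or coordinator, for withdrawal only.
- Section 16 (Risk to Participants): questions may be skipped; no contact is given.
- Section 20: no DSMB.

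The employee health service is thus the only contact that the protocol names for symptoms across all three arms.

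**3. How many are affected?** The instruction reaches all 150 planned participants. The subset unable to use the service lies somewhere between none and all of them. The documents give no breakdown by employer, athlete status or age 15 to 17 that would narrow this.

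**The case against.** The strongest reply is that these are active surgical patients, not people left to a handout. Every arm sees the surgical team three times in 3 months, study staff meet participants at those visits, discharge instructions are issued, and the team may remove a patient to protect that patient's health. The study is described as minimal risk. The handout itself is not among the documents and may already list usable contacts. Some participants may also have an employee health service of their own. All of this stands, and it keeps the point small. It does not make the written instruction suit the population.

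A reader might infer three stronger things that the documents do not support:

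- **That participants must rely on this contact to reach care.** Section 21 says only that study symptom data are not acted on in real time. It does not make the handout the sole route to clinical help.
- **That control participants lack mental-health support.** Directed referral is described only for the specialist arms, but the control-arm text describes standard pain care. Its silence does not show that other care is absent.
- **That participants are not told that opting out leaves their clinical care unaffected.** Section 23 (Informed Consent) summarises a script and mentions employment, not clinical care. The consent form was removed from the material available for review and may well carry that assurance, so no omission can be claimed.

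Section 23 also says that people who opt out may still take part in training, although no study component bears that name. Section 6 does say that all participants are trained to wear the actigraphy device, so the phrase may have an innocent meaning, and no consequence follows from it. Together with the remark about employment, it might suggest text carried over from a study of staff. That is conjecture, and the point does not depend on it.

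**Conclusion.** The point holds as a minor participant-safety correction. Section 21 names an unspecified employee health service as the symptom contact for a patient population that need not be employed by the study institutions and may include minors. Some participants may be unable to use it. The number is unknown, and surgical follow-up and discharge instructions limit the consequence.

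The conclusion rests on two assumptions: that an employee health service generally restricts access to its own employer's staff, and that the handout follows the protocol wording. If the handout already gives contacts that any patient can use, only the protocol sentence needs correcting. No endpoint, randomisation, sample size or analysis is affected.

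**What to change.** In Section 21, replace the employee health service with contacts open to every participant: the orthopaedic clinical team, plus mental-health or crisis resources, including ones suitable for ages 15 to 17. If an employee service is intended for some participants, say whose it is and list it as an additional contact. Check that the handout in use matches the amended text. The reference to training in Section 23 can be clarified at the same time as a tidy-up.

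The cost is a small IRB wording amendment and a revised handout.

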**22. Economic Burden to Participants**

There is no cost for participants to be in this study.

**23. Informed Consent**

Consent will be given in person or as e-consent in RedCap at baseline, which will occur in a private space within Emory Healthcare or Grady. If the patient is between the ages of 15 to 17 years, the informed consent discussion will also include one of the patient's parents/legal guardians. For these cases, we will require the signature of the subject's assent and the signature of the person soliciting assent of the subject.

**Protocol Title:** Implementing and Evaluating the Effect of Personalized Pain Coaches After Orthopaedic Surgery for Patients with Sports Medicine Injuries to Improve Postoperative Outcomes

---

The study staff will provide an overview of the study's purpose, benefits, anticipated risks, and copies of the consent if requested with the surveys and be available to read the consent or answer any questions participants may have. The script, as well as the coordinator, will emphasize in the verbal instructions that the study is voluntary and that participants may opt out of the study or surveys at any time point and still participate in the training. Further, individuals will be told that opting out of any surveys or study components will not impact their employment.

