#### **5. Study Intervention/Design**

Patients will be randomized to either:

- (1) In person LCS intervention** - With *Opioid Risk Education*, patients will receive opioid education after completing the validated Opioid Risk Tool (ORT), a detailed substance abuse survey and mental health screening, and Naloxone education. *Therapeutic Intervention* will include the Community Resiliency Model (CRM). *Clinical Pain Coordination* will include directed referrals for complex needs, including mental health and substance use disorders, as needed. In addition to above mentioned 3 intervention components, all patients in the LCS intervention arm will also receive the current standard-of-care. The Community Resiliency Model (CRM) is a noncognitive variant of mindfulness, emphasizing attunement to interoceptive and exteroceptive signaling cues for regulation of autonomic responses to stress (Grabbe, Higgins, Baird, Craven & San Fratello, 2020). CRM was derived from somatic psychotherapy and self-stabilization interventions using body sensation awareness. Body sensation awareness is called introspection and is a key component of mindfulness. Awareness of internal body sensation occurs in the insular cortex and adjacent brain structures, which serve as cerebral centers regulating emotional regulation, empathy, and social interaction (Simmons et al., 2013). Implementing these techniques may preventatively attenuate the immediate impact of stressors. For example, the CRM model has been implemented across several settings and populations and has been associated with improved well-being, resiliency, and physical symptoms (Grabbe et al., 2020; Grabbe et al., 2021; Habimana et al., 2021). CRM skills are introduced over a sixty-to-ninety-minute session, allowing for a brief introduction and application of skills by participants.

- (2) **Virtual LCS intervention** - With *Opioid Risk Education*, patients will receive opioid education after completing the validated Opioid Risk Tool (ORT), a detailed substance abuse survey and mental health screening, and Naloxone education. *Therapeutic Intervention* will include the Community Resiliency Model CRM).. *Clinical Pain Coordination* will include directed referrals for complex needs, including mental health and substance use disorders, as needed. In addition to above mentioned 3 intervention components, all patients in the LCS intervention arm will also receive the current standard-of-care.

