- (3) **No LCS intervention** - Patients will receive the current standard-of-care for pain management in the aftermath of surgery, which includes: a standardized prescription protocol, hospital-system approved discharge instructions which provide written instruction on how to taper opioid use, links to written/online resources for opioid misuse, overdose prevention, and State-approved disposal options.

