#### **15. Withdrawal of Participants**

Individuals may withdrawal from the study at any point by emailing the PI or study coordinator. A patient may also be withdrawn/removed by the study team, if necessary, to protect the patient's health. Once a patient withdraws, the reason will be documented.

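### The consent script promises every participant an undefined training after opting out, and the protocol does not say what an opt-out ends

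*Combined protocol and SAP*

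**What the plan says.** Section 23 (Informed Consent) requires the script and the coordinator to emphasise that "participants may opt out of the study or surveys at any time point and still participate in the training". The sentence has no limit by arm. The one after it tells people that "opting out of any surveys or study components will not impact their employment", and Section 21 adds that "All participants will receive a handout with the contact information of employee health services", although the participants are surgical patients.

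Section 6 sets the order: "If informed consent is obtained, they will be enrolled into REDCap for randomization into one of the three groups".

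Section 5 describes the two LCS arms, in which "CRM skills are introduced over a sixty-to-ninety-minute session" alongside opioid education and pain coordination. Of the third arm it says: "Patients will receive the current standard-of-care for pain management in the aftermath of surgery".

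Section 15 says only "Individuals may withdrawal from the study at any point by emailing the PI or study coordinator", that the team may remove a patient to protect health, and that the reason is recorded. It does not separate stopping the intervention from stopping data collection.

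**The concern.** A consent statement should be true for everyone who hears it and should fit the design. This one offers something the protocol does not define to people of whom a third of the allocation options (one arm in three) receives no LCS content. If it is heard as an offer of the LCS or Community Resiliency Model (CRM) session, there are two problems. Controls are told that they may have something they are not allocated. LCS participants are told that they may give up the surveys and keep whatever LCS contact remains.

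That is the less useful way round for a trial. The primary objective in Section 1 is patient-reported pain, which is collected mainly by survey. The plan needs a participant to be able to stop the intervention or a device and still be followed. At present the script protects the training and gives up the data, and no section provides the reverse.

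**Working it through.** This is a question of wording, so the check sets the sections side by side. The protocol's only planning figure is the sample size of 150. It is given without alpha, power, effect size or attrition, so there is no figure to reproduce.

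**1. Who hears the statement.** Section 6 puts consent before randomization, and Section 23 names no arm. Every participant hears it, including future controls.

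**2. What the training could be.**

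| Reading | Support in the protocol | Consequence |
|---|---|---|
| LCS/CRM session | Section 5 describes a skills session in two of the three arms; Section 3 speaks of patients lacking training in non-drug pain methods. Neither the intervention text nor Section 23 makes the link. | Either untrue for controls or in conflict with allocation |
| Actigraphy wear | Section 6 says that participants in all arms are trained to wear the device | No conflict with allocation, but little sense in offering it to someone who has left |
| Text from another study | Employment wording in Section 23; employee health handout in Section 21 | Nothing in this trial answers to the promise |

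The third reading is the most probable, because the two employee references fit no part of this trial. It is an inference and not proven. Under none of the three does the clause serve a purpose here.

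**3. When the clause would add to an ordinary right to withdraw.** The sequence in Section 6 is consent, allocation, baseline measures, LCS session, surgery, then surveys at 2 weeks, 6 weeks and 3 months. The LCS session takes place at the preoperative consult or "at another time no later than 24 hours before surgery". Anyone who leaves after it has already had it. The clause therefore adds something only in two windows:
- between allocation and the session;
- after surgery, if LCS contact continues. Section 3 describes the role as extending through recovery and Section 5 allows referrals as needed, but Sections 5, 6 and 9 schedule no postoperative LCS visit.

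**4. What an opt-out from surveys would remove.** It removes the PROMIS and other survey outcomes. Inpatient pain ratings and opioid doses from the health record, the electronic pill-cap data, and actigraphy to the 2-week visit could remain.

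**5. Size, as illustration only.** No rate below is in the documents. Assumptions: 1:1:1 allocation (50 per arm; the ratio is not stated), SD 10 T-score points (the population norm quoted in Section 6), two-sided alpha 0.05, 80% power.
- Detectable difference, both LCS arms against control: 10 × (1.960 + 0.842) × √(1/100 + 1/50) = 4.85 points. If only LCS participants are lost, at 10%, 20% or 30%, it becomes 4.94, 5.05 or 5.19.
- Complete-case shift in an arm = fraction lost × difference between leavers and stayers. With 20% lost in LCS, 10% in control and a 5-point difference: 0.20 × 5 − 0.10 × 5 = 0.5 points. With a 10-point difference: 0.20 × 10 − 0.10 × 10 = 1.0 point.
- If a fraction c of controls took up the session with full effect, the contrast shrinks by the factor (1 − c). Power for an assumed 5-point difference falls from 82% to 74%, 64% or 52% at c = 0.10, 0.20 or 0.30.

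Nothing in the documents attributes any such loss or crossover to this clause.

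**The case against.** The best defence is that this is leftover text with little practical effect. Much of that stands, and it rules out several stronger readings that a reader might infer.

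- *That the training is the LCS session.* The protocol does not say so. The only instruction of trial participants that it calls training is how to wear the actigraphy device.
- *That Sections 15 and 23 contradict each other.* Section 15 does not say that leaving ends everything. It says nothing on the matter, which is a gap.
- *That LCS participants would drop the outcomes and keep the treatment.* The one scheduled session comes before every postoperative outcome. The second $50 in Section 18 depends on completing the study and returning equipment, which works against opting out. Section 6 also provides email, telephone, post and QR-card routes for uncompleted measures.
- *That controls will cross over.* No section gives a control an LCS session.
- *That there is a bias of known size.* The rates in the illustration are assumed. Even then, 0.5 points is about a tenth of the 4.85-point detectable difference, and the mixed models in Section 19 can use partial follow-up. The absence of an intention-to-treat or missing-data rule in Section 19 is a separate gap.

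The script and consent form are also not among the documents, so the term may be defined there.

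What the defence does not reach is the statement itself. Section 23 is current text and directs staff to emphasise it. If it is leftover, participants, including those aged 15 to 17 and their parents, are promised something that does not exist in this trial. If it is meant, it does not fit the control arm.

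**Conclusion.** The concern holds as a defect of consent wording together with a missing follow-up rule. All participants are told before allocation that an undefined training stays open to them after opting out, while one arm of three is allocated standard of care only. The text was probably carried over from a workplace study. The conflict with allocation depends on the training being heard as the LCS/CRM session, which is plausible to a patient but not stated.

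The likely effect on the results is small, because the scheduled session precedes surgery, and it cannot be quantified from the documents. The correction is still worth making: it removes a statement that is untrue or unclear, and it protects survey-based primary outcomes at very low cost.

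**What to change.** - In Section 23 and the script, delete the closing clause that keeps the training open to those who opt out, and delete the employment wording. In Section 21, correct the reference to employee health services.
- In Sections 15 and 23, state one rule for all arms: stopping LCS contact or devices does not end follow-up. Such participants are asked to continue the 2-week, 6-week and 3-month surveys. Abstraction of opioid data from the health record continues unless consent or authorisation for it is withdrawn.
- On the withdrawal form, record which of these elements the participant has stopped.

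The cost is a minor IRB amendment and a small change to the withdrawal form. No visits or procedures are added.
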